3.8. TREATMENT ASSIGNMENT & BLINDING

3.8.1. Treatment Assignment

The study will be conducted in multiple investigative sites and will involve variable numbers of subjects at each site. Enrollment will be on a competitive basis, but each site will be capped at 68 randomized subjects. Activation of investigational sites will be centrally controlled by IWRS.

Subjects who meet the eligibility criteria required at the screening visit (visit 1) must be registered in the IWRS in order to be assigned a subject number and a bottle of run-in drug. During the study treatment periods, a new bottle will be assigned to the subject every 12 weeks by the IWRS at visits 3, 6, and 9. There are two randomization procedures planned in this study, at visit 3 and visit 9.

Subjects who complete the run-in period and meet the ABPM SBP ≥ 135 mm Hg criterion at visit 3 will be randomized to receive a bottle of bexagliflozin, 20 mg or placebo. Subjects will be assigned to each group in a 1:1 ratio. Randomization will be stratified according to diabetes status (history of type 2 diabetes or not), baseline ABPM SBP (≥ 160 mm Hg or not), unmedicated or not, and renal function (eGFR ≥ 60 or not). The investigator or designated staff will log into the IWRS to receive the randomization code and assigned kit number for bexagliflozin tablets, 20 mg or placebo.

At visit 6 after a subject has completed the ABPM successfully, a second bottle of study drug will be assigned to the subject by IWRS. All subjects will receive active treatment for the following 12 weeks. Subjects who experience persistent hypertension during the first 12 weeks of treatment may complete visits 5 and 6 prior to week 12.

At visit 9 after a subject has completed the 24 h ABPM successfully, the subject will be randomly assigned to receive either bexagliflozin or placebo. A new randomization number and a new bottle of double blind study drug will be assigned and dispensed to the subject. Assignment to the active or control arm will be balanced to approximately equalize the representation in each arm of the following groups:

- Subjects not requiring rescue medication prior to week 24 and exhibiting a > 20 mm Hg reduction in mean SBP between cumulative weeks 1 and 24;
- Subjects not requiring rescue medication prior to week 24 and exhibiting a > 5 mm Hg and ≤ 20 mm Hg reduction in mean SBP between cumulative weeks 1 and 24;
- Subjects not requiring rescue medication prior to week 24 and exhibiting a ≤ 5 mm Hg reduction in mean SBP between cumulative weeks 1 and 24;
- Subjects requiring rescue medication prior to week 24.

If the mean SBP is missing at cumulative week 24, the subject will be withdrawn.

Subject randomization will be deactivated for all sites when the planned number of subjects is met and a minimum of 10% of the subjects have an average 24 h ABPM SBP ≥ 160 and < 180 mm Hg at visit 3. However, if a potential subject has started the run-in period at that time and wishes to continue to participate, the subject will be allowed to continue and, if eligible, to be randomized.

3.8.2. Blinding

Both studies will have double-blind treatment phases. The sponsor study management team, investigators, study coordinators, pharmacists, study subjects and cardiovascular endpoint committee (CEC) will be blinded to the study medications. Protocol section 5.5 provides the general rule to maintain blinding of the individual treatment assignment.

There are periodical data safety monitoring reports and meetings planned for THR-1442-603. A designated unblinded statistician who is not involved with the study operation will hold the treatment codes and prepare reports to facilitate these activities. A separate data and safety monitoring board statistical analysis plan contains details for the types of analyses required and procedures to preserve blinding to treatment assignment.

A planned interim futility analysis was conducted by the unblinded statistician and an independent Data Monitoring Committee (DMC) after 50% of the randomized subjects received at least 12 weeks of treatment to evaluate the effectiveness of bexagliflozin. All study subjects were to continue to receive the investigational products during the data cleaning and analysis time. The unblinded statistician was responsible for preparation of the interim analysis report. The same procedures specified in the safety monitoring board statistical analysis plan were followed to preserve blinding and handle accidental unblinding.

3.9. ADMINISTRATION OF STUDY MEDICATION

The study subject will take one tablet per day of the following investigational products in addition to background medications such as treatments for diabetes, hyperlipidemia, or hypertension:

- Run-in period: placebo run-in medication
- Study 603A: bexagliflozin tablets, 20 mg or placebo
- Study 603B week 1 to week 12: bexagliflozin tablets, 20 mg only
- Study 603B week 13 to week 24: bexagliflozin tablets, 20 mg or placebo

The integrated dosing schedule is illustrated in Figure 1.

[figure not shown]

Figure 1 THR-1442-C-603 Study Design

3.10. STUDY PROCEDURES AND FLOWCHART

The activities that must be performed at each clinic visit listed below are presented in Table 1.

A visit window of ± 3 days is allowed for all post-randomization visits. Visit 3 is the day of randomization and the basis for the visit window. A repeat ABPM shall be performed within 2 days if the 24h-ABPM is incomplete. Only the second set of ABPM data will be entered in the case report form on visits 2-3, 5-6, 8-9, and 10-11. The other specified procedures in the same assessment period do not need to be repeated. If the ABPM fails twice at visit 3 prior to randomization, the subject is considered a screen failed subject. If the ABPM cannot be completed successfully twice after randomization, the ABPM BP for that assessment period is considered missing.

Procedures listed for visit 10 and 11 will be completed if a subject is withdrawn from the study.

Table 1 Schedule of Events

Procedures	Screening/ Run-in		Study 603A			Study 603B					
			Weeks 1 to 12			Weeks 1 to 12			Week 13 to 24		
Cumulative study week			1-12			13-24			25-36		
Visit Number	1	2	3	4	5	6	7	8	9	10	11
Time to first randomization	-13 or -12 d	-1d	0w +1d	6w	12w	12w +1d	18w	24w	24w +1d	36w	36w +1d
Informed Consent	x										
Medical History	x										
Inclusion/Exclusion Criteria	x	x	x								
Run-in drug dispensation	x										
Randomization			x						x		
Begin 24-h ABPM		x			x			x		x	
End 24-h ABPM			x			x			x		x
Double blind drug dispensation			x			x			x		
Whole blood sample	x	x			x			x		x	
Hematology	x	x			x			x		x	
HbA1c	x	x			x			x			
Serum sample										x	
Chemistry	x	x			x			x		x	
Lipids	x	x			x			x		x	
Urine sample											
Urinalysis	x	x			x			x		x	
Pregnancy test (WCBP)	x	x			x			x		x	
Population PK Sampling							x	x			
12-Lead ECG	x	x			x			x		x	
Vital Signs	x	x	x	x	x	x	x	x	x	x	x
Abbreviated PE & weight	x				x			x		x	
Complete PE & weight		x									
Adverse Events Assessments		x		x	x		x	x		x	x
Concomitant Medication Assessments		x		x	x		x	x		x	x

4. ENDPOINTS

4.1. STUDY 603A

4.1.1. Primary Efficacy Endpoint

- Change from baseline (Day 1) to week 12 of the 24-hour mean SBP.

4.1.2. Secondary Efficacy Endpoints

- The proportion of subjects who achieve a reduction of mean ambulatory SBP of 10 mm Hg or greater;
- The proportion of subjects who achieve a mean ambulatory SBP of 135 mm Hg or less;
- The trough-to-peak ratio of ambulatory SBP at week 12;
- The placebo-adjusted change from baseline to week 12 in seated office SBP;
- The proportion of subjects who achieve a mean seated office SBP of 140 mm Hg or less at week 12;
- The placebo-adjusted change in mean ambulatory DBP from baseline to week 12;
- The proportion of subjects who achieve a mean ambulatory DBP of 87 mm Hg or less at week 12;
- The proportion of subjects who achieve a reduction of mean ambulatory DBP of 4 mm Hg or greater;
- The placebo-adjusted change from baseline to week 12 in seated office DBP;
- The proportion of subjects who achieve a mean seated office DBP of 90 mm Hg or less at week 12;

4.1.3. Exploratory Efficacy Endpoints

To further assess treatment effect in key subset populations as well as clinically relevant measurements associated with blood pressures, following exploratory efficacy endpoints will be analyzed.

- The placebo-adjusted change from baseline in the 24-hour mean ambulatory SBP at week 12 for subjects who had three or more types of antihypertensive therapies at baseline;
- The placebo-adjusted change from baseline in 24-hour mean pulse pressure at week 12;

- The placebo-adjusted change from baseline to week 12 in 24-hour mean ambulatory SBP (among dippers, and among non-dippers);
- The placebo-adjusted change from baseline to week 12 in 24-hour mean ambulatory heart rate (HR);
- The placebo-adjusted change from baseline to week 12 in body weight;
- The placebo-adjusted change from baseline to week 12 in HbA1c;
- The proportion of subjects requiring any rescue medication at week 12.

4.2. STUDY 603B

4.2.1. Primary Efficacy Endpoint

- Change from baseline week 12 (cumulative week 24) to week 24 (cumulative week 36) of the 24-hour mean SBP.

4.2.2. Secondary Efficacy Endpoints

- The placebo-adjusted change from week 12 to week 24 in seated office SBP;
- The placebo-adjusted change in mean ambulatory DBP from week 12 to week 24;
- The placebo-adjusted change from week 12 to week 24 in seated office DBP.

4.2.3. Exploratory Efficacy Endpoints

To further assess treatment withdrawal effect, following exploratory endpoints will be analyzed.

- The placebo-adjusted change from baseline week 12 to week 24 in 24-hour mean ambulatory SBP by baseline week 12 response status (rescued, >20 mm Hg, >5 and ≤20 mm Hg, ≤5 mm Hg, and >5 mm Hg);
- The proportion of subjects requiring any rescue medication at week 24.

4.3. INTEGRATED ANALYSES

Assessments for studies 603A and 603B will be combined to further assess the effectiveness of bexagliflozin after treatment of 12, 24, and 36 weeks.

There are four (4) separate treatment sequences after combining studies 603A and 603B (Table 2).

Table 2 Treatment Sequences for combined studies 603A and 603B

Sequence	Period 1	Period 2	Period 3
Seq 1 PBB	(603A) placebo	(603B) bexagliflozin	(603B) bexagliflozin
Seq 2 PBP	(603A) placebo	(603B) bexagliflozin	(603B) placebo
Seq 3 BBB	(603A) bexagliflozin	(603B) bexagliflozin	(603B) bexagliflozin
Seq 4 BBP	(603A) bexagliflozin	(603B) bexagliflozin	(603B) placebo

The following secondary endpoints will be assessed:

- Change in mean ambulatory SBP or DBP after 12 weeks treatment with bexagliflozin using week 12 assessments for Seq 3 or 4 (end of Period 1) and cumulative week 24 assessments for Seq 1 or 2 (end of Period 2);
- Change in mean ambulatory SBP or DBP after 24 weeks treatment with bexagliflozin using cumulative week 24 assessments for Seq 3 or 4 (end of Period 2) and cumulative week 36 assessment of Seq 1 (end of Period 3);
- Change in mean ambulatory SBP or DBP after 36 weeks treatment with bexagliflozin using cumulative week 36 assessments for Seq 3 (end of Period 3);
- Change in seated office SBP or DBP after 12 weeks treatment with bexagliflozin using week 12 assessments for Seq 3 or 4 (end of Period 1) and cumulative week 24 assessments of Seq 1 or 2 (end of Period 2);
- Change in seated office SBP or DBP after 24 weeks treatment with bexagliflozin using cumulative week 24 assessments for Seq 3 or 4 (end of Period 2) and cumulative week 36 assessments for Seq 1 (end of Period 3);
- Change in seated office SBP or DBP after 36 weeks treatment with bexagliflozin using cumulative week 36 assessments for Seq 3 (end of Period 3).
- Cumulative mean change from baseline in seated office SBP as a function of time (including all scheduled office visits) for subjects exposed to bexagliflozin
- Cumulative mean change from baseline in seated office DBP as a function of time (including all scheduled office visits) for subjects exposed to bexagliflozin

4.4. SAFETY ENDPOINTS

- Treatment emergent adverse events
- Treatment emergent adverse events of special interest
- Concomitant medication use

- Laboratory test
- Cardiac rhythm determined by 12-lead ECG
- Vital signs
- Physical examination

5. ANALYSIS SETS

5.1.1. Study 603A

The following analysis sets will be analyzed:

- Intention-to-Treat (ITT) Analysis Set: will include all subjects who are randomized to the study. All subjects will be analyzed according to the treatment to which they were randomized to receive.
- Safety Analysis Set: will include all subjects who are randomized to the study and have taken at least one dose of double blind investigational product. This analysis set will be used for study 603A safety analyses. All subjects will be analyzed according to the treatment they receive.

5.1.2. Study 603B

- ITT Analysis Set: will include all subjects who are randomized at week 12. All subjects will be analyzed according to the treatment to which they were randomized to receive.
- Safety Analysis Set: will include all subjects who have taken at least one dose of investigational product.
- Safety Analysis Set for withdrawal period: will include all subjects who are randomized at week 12 and have taken at least one dose of double blind investigational product. All subjects will be analyzed according to the treatment they receive.

5.1.3. Integrated Analyses

- Integrated ITT Analysis Set: will include all subjects who are randomized to bexagliflozin in 603A, or entered study 603B run-in period. The set will include all subjects to whom a study kit is dispensed in 603B run-in period, and subjects who are randomized to bexagliflozin in 603A.
- Integrated Safety Analysis Set: will include all subjects who are treated with at least one dose of bexagliflozin in either study. This will include subjects in the 603B safety analysis set and subjects who received at least one dose of bexagliflozin during 603A.

6. GENERAL ASPECTS FOR STATISTICAL ANALYSIS

6.1. GENERAL METHODS

Statistical methodology and analyses are in accordance with the principles outlined by the ICH E9 guidelines. All statistical analyses will be conducted using SAS statistical software version 9.3 or higher.

Tables, listings and figures (TLFs) will be produced in accordance with the principles outlined by the ICH E3 guidelines. For most summary statistics, data will be analyzed by the following treatment groups: Bexagliflozin 20 mg; Placebo. For 603B, unless otherwise specified, data will be analyzed by treatment in the 603B withdrawal period. Treatment in 603B withdrawal period will be further split by treatment sequence (as shown in Table 2). For integrated analyses, unless otherwise specified, summaries will be by total of all patients in the analysis set.

Data summaries will use descriptive statistics (number of subjects [n], mean, standard deviation [SD], Q1, median, Q3, minimum and maximum) for continuous variables, and frequency and percentage of subjects for categorical and ordinal variables, unless otherwise specified.

Unless otherwise specified, all statistical tests will be two-tailed using a 0.05 level of significance. All confidence intervals (CIs) will be two-sided 95% CIs.

Only scheduled visits will be included in by visit summaries. All visit assessment data will be included in shift tables and will appear in the subject listings.

No data imputation will be applied for missing values in safety analysis. Efficacy data imputation method will be described in Section 8.

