3.3. INTEGRATIVE OBJECTIVES OF STUDY 603A AND 603B

- To assess consistent effects on mean ambulatory SBP/DBP after 12 weeks of bexagliflozin treatment, as well as longer treatment periods, i.e., 24 weeks or 36 weeks of bexagliflozin treatment.
- The seated office systolic and diastolic blood pressure will be collected at more frequent intervals than for ambulatory monitoring, and the changes over time will be evaluated to provide a composite profile of treatment effect as a function of time.

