3.5.1. Study 603A

Study 603A is a double blind, placebo controlled multi-center study. Approximately 680 male and female adult subjects with an office sitting blood pressure ≥ 140 mm Hg and < 180 mm Hg, and who are taking no more than 4 anti-hypertensive medications will be enrolled in study 603A. The overall population should be selected to contain $> 10\%$ of subjects with a baseline ABPM > 160 mm Hg and $< 30\%$ of subjects with type 2 diabetes mellitus.

Subjects who meet the eligibility criteria at the screening visit (visit 1) will start a 2 week run-in period. At the end of the run-in period, subjects who have not been disqualified will be eligible for participation. At the investigative site the subjects will take the last dose of run-in drug, will be fitted with an ABPM device and will start a 24-h ABPM to establish the baseline ABPM SBP and DBP. On the following day, qualified subjects who have completed the 24-h ABPM with a mean 24-h SBP ≥ 135 mm Hg will be randomly assigned to receive bexagliflozin tablets, 20 mg or placebo, using an interactive web response system (IWRS). If < 64 BP readings are recorded, the ABPM must be repeated within 2 days. Prior to randomization, subjects who cannot successfully complete the ABPM within two attempts will be considered screen failures.

A six week visit to the investigational site will allow seated office measures of systolic and diastolic BP to be recorded. At week 12 (end of study), the subject will visit the investigational site, consume the final tablet, and be fitted for ABPM.

An interim non-binding futility analysis is planned when 50% of the randomized subjects (i.e., 300) have completed study 603A.

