6.2. KEY DEFINITIONS

6.2.1. Baseline Values

Unless otherwise specified, baseline is defined as:

- For study 603A endpoints, baseline is defined as the last non-missing measurement prior to the first dose of double-blind study medication in 603A.
- For study 603B endpoints, baseline is defined as the last non-missing measurement prior to the first dose of double-blind study medication in 603B.
- For integrated endpoints by weeks from first exposure to bexagliflozin, baseline is defined as the last non-missing measurement prior to the first exposure of bexagliflozin. Considering the 4 sequences in Table 2, baseline for Seq 3 or 4 is the

last non-missing measurement prior to first dose of bexagliflozin in 603A. Baseline for Seq 1 or 2 is defined as the last non-missing measurement prior to the first dose of bexagliflozin in 603B run-in period. This applies to all integrated efficacy endpoints or the safety summaries by weeks of bexagliflozin treatment.

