8.3. INTEGRATED ANALYSES

Assessments for studies 603A and 603B will be combined to further assess the effectiveness of bexagliflozin after treatment for 12, 24, and 36 weeks. The sequence numbers in this section refer to the numbers in Table 2. All analyses will be based on the integrated ITT analysis set.

8.3.1. Change in mean ambulatory SBP or DBP after 12, 24, and 36 weeks of treatment of bexagliflozin

Summary statistics will be provided for actual value at baseline, and actual value and change from baseline after 12, 24, and 36 weeks treatment with bexagliflozin. The 95% CI based on normal distribution will also be presented for the change value. For subjects who require rescue medication, the ABPM taken prior to rescue medication (as was used for the primary analyses for studies 603A and 603B) for the time point will be used.

The proportion of subjects who achieve defined goals will be summarized after 12, 24, and 36 weeks treatment with bexagliflozin using frequency, percentage and 95% binomial confidence interval. These goals will include:

- A reduction of mean ambulatory SBP of 10 mm Hg or greater;
- A reduction of mean ambulatory DBP of 4 mm Hg or greater.

8.3.2. Change in seated office SBP or DBP after 12, 24, and 36 weeks treatment of bexagliflozin

Summary statistics as in section 8.3.1 will be provided for seated office SBP or DBP. The proportion of subjects who achieve defined goals will be summarized after 12, 24, and 36 weeks treatment with bexagliflozin using frequency, percentage and 95% binomial confidence interval. These goals will include:

- The proportion of subjects who achieve a mean seated office SBP of 140 mm Hg or less at week 12.
- The proportion of subjects who achieve a mean seated office DBP of 90 mm Hg or less at week 12.

8.3.3. Cumulative mean change from baseline in seated office SBP and DBP as a function of time (including all scheduled office visits) for subjects exposed to bexagliflozin

Summary tables will be presented for seated office SBP and DBP by treatment sequence for all subjects in 603B ITT population. Table will include baseline, actual value and change from baseline at cumulative weeks 6, 12, 18, 24, and 36. Baseline is defined as the last non-missing value before the first dose of bexagliflozin in 603A. A by-sequence plot of change from baseline will include mean and standard error.

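### The integrated ambulatory summaries carry regression to the mean in a share that rises from 12 to 36 weeks, so a constant drug effect can appear to grow

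*SAP*

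**What the plan says.** **Layout.** SAP 6.1 sets the default: "For integrated analyses, unless otherwise specified, summaries will be by total of all patients in the analysis set". Section 8.3.1 gives no other layout for the ambulatory summaries. It plans values and changes from baseline after 12, 24 and 36 weeks of bexagliflozin, and adds: "The 95% CI based on normal distribution will also be presented for the change value". It also plans the proportions with a fall of at least 10 mm Hg in ambulatory SBP or at least 4 mm Hg in ambulatory DBP. Section 4.3 lists the changes as secondary endpoints.

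**Baselines (SAP 6.2.1).** For Seq 3/4 (BBB, BBP) the baseline is the "last non-missing measurement prior to first dose of bexagliflozin in 603A". For the others: "Baseline for Seq 1 or 2 is defined as the last non-missing measurement prior to the first dose of bexagliflozin in 603B run-in period". For ambulatory pressure that is the 603A week-12 recording, made on placebo.

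**Selection (SAP 3.5.1).** At the end of the run-in, subjects "will start a 24-h ABPM to establish the baseline ABPM SBP and DBP", and "qualified subjects who have completed the 24-h ABPM with a mean 24-h SBP ≥ 135 mm Hg will be randomly assigned". The reading that qualifies a subject is therefore also the baseline for Seq 3/4. The week-12 recording has no such threshold.

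**Composition (SAP 4.3).** The 12-week change is formed "using week 12 assessments for Seq 3 or 4 (end of Period 1) and cumulative week 24 assessments for Seq 1 or 2". The 24-week change uses Seq 3/4 at cumulative week 24 and Seq 1 at cumulative week 36. The 36-week change uses Seq 3 only.

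**Aim (SAP 3.3).** "To assess consistent effects on mean ambulatory SBP/DBP after 12 weeks of bexagliflozin treatment", and after the longer periods of 24 and 36 weeks.

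**The concern.** A reading that had to exceed a threshold is, on average, above the subject's usual level, so a repeat reading falls without any drug effect. In 603A both arms share this fall and randomization removes it. The integrated summaries have no control, so in Seq 3/4 the fall is counted in a change presented as effectiveness.

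The two kinds of baseline are combined in proportions that differ at each duration. If the drug effect were the same at 12, 24 and 36 weeks, the reported change could still rise, because the share of subjects with a thresholded baseline rises. Maintenance over longer treatment is what these summaries are meant to describe, and one total column gives no means of separating a real trend from a change of mix.

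**Working it through.** **The plan's own figures (SAP 3.7).** For 603B, n per arm = 2 × (1.960 + 1.036)² × 15² / 4² = 252.5, so 253 (254 by t-test; stated 254). Allowing for 75% completion, 508 / 0.75 = 677.3, so 678 (stated 680). At the end of 603A, 680 × 0.92 = 625.6 (stated 626), and 313 per arm gives power 0.986 for 5 mm Hg with SD 15 (stated >95%). These reproduce. The plan gives no figure for the integrated summaries.

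**Share with the thresholded baseline.** Start from 340 per 603A arm (680 at 1:1), with 92% remaining at week 12 and 75% at week 36. Retention at week 24 is not given; I assume 80 to 87%, with midpoint 83.5%.

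| Duration | Seq 3/4 | Placebo-first | Share from Seq 3/4 |
|---|---|---|---|
| 12 weeks | 340 × 0.92 = 313 | 340 × 0.835 = 284 | 313 / 597 = 52% (51 to 54%) |
| 24 weeks | 340 × 0.835 = 284 | 340 × 0.75 / 2 = 128 (Seq 1) | 284 / 412 = 69% (68 to 70%) |
| 36 weeks | 340 × 0.75 / 2 = 128 (Seq 3) | 0 | 100% |

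**Regression to the mean in Seq 3/4.** Take a normal ABPM mean with population mean μ, between-subject SD b, within-subject SD w and total SD σ = √(b² + w²). With entry at 135 or above and a = (135 − μ)/σ, the expected fall is (w²/σ) × φ(a)/(1 − Φ(a)). The documents give none of these inputs. Assume b = 10 to 12, w = 7 to 10 and μ = 138 to 146 mm Hg.

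- Low end (b = 10, w = 7, μ = 146): σ = 12.21, a = −0.90, φ/(1 − Φ) = 0.326, fall = 49/12.21 × 0.326 = 1.3 mm Hg.
- High end (b = 10, w = 10, μ = 138): σ = 14.14, a = −0.21, φ/(1 − Φ) = 0.668, fall = 100/14.14 × 0.668 = 4.7 mm Hg.

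**Pooled bias.** This is share × fall.

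- 12 weeks: 0.524 × 1.3 = 0.7 to 0.524 × 4.7 = 2.5 mm Hg.
- 24 weeks: 0.69 × 1.3 = 0.9 to 0.69 × 4.72 = 3.3 mm Hg.
- 36 weeks: the full 1.3 to 4.7 mm Hg.

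**Wider assumptions.** With total SD 10 to 15, test-retest correlation 0.5 to 0.9 and 10 to 20% of entrants at 160 or above (SAP 3.8.1 asks for at least 10%), the fall in Seq 3/4 runs from 0.1 to 5.8 mm Hg. SD 15 with correlation 0.5 implies an SD of change of 15 × √(2 × 0.5) = 15, the plan's value, and gives 3.4 to 5.8.

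**Apparent time trend.** Suppose a true effect of 5 mm Hg at every duration. The reported reduction is 5 + share × fall:

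| Fall in Seq 3/4 | 12 weeks | 24 weeks | 36 weeks | False rise |
|---|---|---|---|---|
| 1 | 5.5 | 5.7 | 6.0 | 0.5 |
| 3 | 6.6 | 7.1 | 8.0 | 1.4 |
| 5 | 7.6 | 8.5 | 10.0 | 2.4 |

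**Responder rate (SBP fall of at least 10 mm Hg, no drug effect).** Without selection the probability is 1 − Φ(10/(w√2)): 16% at w = 7 and 24% at w = 10. Simulating the selected baseline under the main assumptions (2 million subjects per setting) gives 18 to 34%. Selection itself therefore adds about 3 to 10 percentage points in Seq 3/4.

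**The case against.** Four stronger readings are tempting, and the documents do not support them.

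- **Pooling creates the bias.** It does not. The cause is an uncontrolled change from a thresholded reading, and adding placebo-first subjects dilutes it. At 36 weeks nothing is pooled and the bias is carried in full. What pooling does is hide the bias and make its weight vary.
- **The whole 1.3 to 4.7 mm Hg, or an 18 to 34% responder rate, is the error in the pooled column.** The first is the Seq 3/4 figure alone. Most of the second is measurement noise, which would occur in Seq 1/2 as well.
- **The office-pressure summaries in 8.3.2 share the problem.** Their goals are absolute (SBP 140 or less, DBP 90 or less) and do not depend on baseline. Office pressure is gated at visits 1 and 2 but measured again at visit 3, so any carry-over into office change should be smaller.
- **The placebo-first baseline is free of selection.** It has no entry threshold, but persistent hypertension can bring visits 5 and 6 forward (SAP 3.8.1). The effect is probably small.

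The best defence is that these results are descriptive, are never called placebo-adjusted and carry no test. The 603A change is already reported by arm (8.1.1.1), the integrated baseline table is split by 603A arm (7.3), and the office profile over time is by sequence (8.3.3). The table shells are separate and might add columns, and the consistency sought in 3.3 may mean consistency across durations. All of that limits the consequence. It does not split the ambulatory 12-, 24- and 36-week summaries, and consistency across durations is exactly what a shifting mix obscures.

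**Conclusion.** The point holds as a presentation fault in the ambulatory summaries of SAP 8.3.1. They are uncontrolled, and they carry regression to the mean from Seq 3/4 in a share of about 52%, 69% and 100% at 12, 24 and 36 weeks. A constant effect can therefore look as if it grows. The shares rest on the plan's attrition and the assumed week-24 retention.

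The size rests on assumed ABPM variability. The main assumptions give a pooled excess of about 0.7 to 2.5 mm Hg at 12 weeks and 0.9 to 3.3 at 24 weeks. If 24-hour ABPM is highly repeatable, the fall is below 1 mm Hg even in Seq 3/4. The additional office-pressure entry criterion is not modelled, and the diastolic carry-over is not quantified.

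A reader should not infer any fault in the primary results. The randomized comparisons of 603A and 603B are unaffected.

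**What to change.** In SAP 8.3.1:

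1. Present the ambulatory changes and responder rates separately for drug-first (Seq 3/4) and placebo-first (Seq 1/2; Seq 1 at 24 weeks) subjects.
2. Beside the drug-first 12-week column, show the 603A placebo-arm change and responder rate.
3. Label any pooled change as uncontrolled.
4. Compare 12, 24 and 36 weeks only within the same subjects, for example Seq 3.

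The office-pressure goals in 8.3.2 need no change. The cost is extra columns in tables already planned. No new data are needed, and the 603A placebo results are already produced under 8.1.
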